7.2 SECONDARY OBJECTIVES

- To study the feasibility, sensitivity, and turnaround time of plasma NGS in lung cancer patients with ALK TKI resistance.
- To study the outcomes of patients with ALK TKI resistance depending upon resistance mechanism detected and subsequent therapy received.
- To study the relationship between plasma NGS results from plasma specimens to advanced ALK positive NSCLC subjects on progression to a next generation ALK TKI and treatment decisions.
- To explore the ability of plasma genotyping to identify novel ALK resistance mechanisms.

Title: Study of Plasma Next Generation Sequencing for Remote Assessment,
Characterization, Evaluation of Patients With ALK Drug Resistance (SPACEWALK)

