8 STUDY DESIGN

8.1 REMOTE CONSENT & PLASMA NGS

Our overarching hypothesis is that we can conduct a remote consent study using plasma NGS to characterize ALK resistance mechanisms arising in ALK positive NSCLC patients with progression while on a next generation ALK TKI, and that the chances of response to further treatment with a different ALK TKI can be predicted using those plasma NGS results.

This study will attempt to prospectively assess the resistance mechanisms detected by a plasma NGS assay in patients with advanced ALK positive NSCLC and systemic progression outside the brain using a web-based remote consent form process. Subjects will be sent blood collection kits with the necessary materials for local draws and those specimens will be sent directly by the subjects to the central laboratory (Resolution Bioscience) for plasma NGS. Plasma NGS results will be returned to the subject, their treating physician and study team, aiming to be returned within 2 weeks by Resolution Bioscience. This will allow prospective characterization of ALK resistant mutations arising in subjects after progression on different specific ALK TKIs. In addition, subsequent treatments and radiologic assessments received by the subjects will be prospectively monitored. A correlation between the ALK resistance mechanisms present at baseline, treatments received before and after plasma NGS assessments and outcomes will be analyzed.

We further propose here that plasma NGS could grant the ability to non-invasively detect specific ALK resistance mutations and, therefore, predict the sensitivity to different ALK TKIs and patients' outcomes. However, prospective CT-based response assessment is not feasible with a remote participation approach. We will instead use time to treatment discontinuation (TTD) as an alternate outcome. In collaboration with the US Food and Drug Administration (FDA), we found that TTD closely correlates with PFS outcomes in patients with genomic-driven lung cancer treated targeted therapies (manuscript in development), and is thus, well suited for studies of real-world evidence like ours. As such, we propose to evaluate the next treatment received by the subjects using TTD as the a time endpoint to assess treatment benefit. We also plan to analyze if plasma NGS results have any impact on the treatment decision process and if alterations in other relevant genes can impact subjects' outcomes.

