10.2.2 Intake Form & Medical Record Release Form

After signing the consent form, study participants will be immediately presented with an electronic version of the Intake Form and Medical Record Release Form. The subject can choose to electronically complete the forms or receive them email as described below.

Participants can also receive a screening email (Appendix I) from the study team with an Intake Form (Appendix J) and Medical Record Release Form (Appendix D). The Intake Form collects the subject's contact information, emergency contact information and the treating physician's contact information. Subjects will also be asked to provide pathology reports, medication information and progression information if available. The Medical Record Release Form is DFCI's standard form for obtaining patients' outside hospital medical records.

Upon completing the Intake Form and Medical Record Release Form, subjects will be screened for eligibility by study staff. If eligible, subjects will be registered into the ALCMI's study-specific data repository and assigned a unique subject identification number (see Section 10.2.3). Subjects will also be registered into DFCI's Clinical Trials Management System (CTMS) as per the institution's standard process.

ALCMI's data repository will release an email notification of a new subject to the appropriate study team members such as the study coordinator and Principal Investigator.

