10.4 STUDY QUESTIONNAIRE

A study questionnaire (Appendix B) will be emailed to the subjects after enrollment to obtain information about the subjects' demographics, current condition, cancer history, and exposure history. The purpose is to gain information about the subject that may or may not be included in their medical records, but will allow the study staff to obtain a more complete representation of the patients' cancer history.

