10.5 CLINICAL DATA COLLECTION

A brief interview with the subjects and a review of the medical records provided will be completed for those selected for entry into the study. Data will be entered on the appropriate CRF in the ALCMI Data Repository. A CRF must be completed for each subject who has been enrolled and has signed an informed consent, including those that fail the screening process or are discontinued from the study. The following clinical data will be collected:

- Demographic data: age at diagnosis, age at enrollment, race/ethnicity, smoking history

**Title: Study of Plasma Next Generation Sequencing for Remote Assessment,
Characterization, Evaluation of Patients With ALK Drug Resistance (**SPACEWALK**)**

- Cancer characteristics: pathology, sites of metastatic disease, prior genotyping results
- Cancer history: date of diagnosis, date of advanced disease
- Treatment history: dates of previous surgery, radiotherapy, chemotherapy and targeted therapy

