10.11 STUDY CALENDAR

Table 1: Times showed are estimations and can be adjusted with Principal Investigator approval if needed pending specific subject circumstances.

Visit Schedule	Registration, Enrollment and Visit 1 - Blood Collection		Follow-up Visits 2-5	Follow-up Visits 6-12	Visit 13/End of Study/Early Termination
	Screening ¹	Blood Collection	Up to 4 visits within 12 week window ⁴	Every 3 months from Enrollment ⁷ Visit 6 (+1 month) Visits 7-12 ±1 Month	Study end ³ 24 months -1 Month ⁷
Informed consent	x				
Registration	x				
Review inclusion & exclusion criteria	x				
Baseline blood collection kit		x			
Request medical records & imaging results	x			x ⁶	
Follow-up ⁴			x ⁴	x	x
Receive NGS report			x ⁵		
Send kit for optional blood draw			x ²	x ²	x ²

¹ Screening is permitted to extend as long as 30 days, if necessary.

² Optional blood specimens may be collected 1-3 weeks after initiation of a new therapy as well as when a subject's disease progresses on that therapy, prior to initiating subsequent line of therapy.

³ Subjects will be followed on study for a minimum of 8 months and for a maximum of 24 months if the study remains open or in follow-up, or until death.

⁴ Subjects weekly for 4 weeks, or as necessary per the subject's treatment plan. It is expected that at least two but no more than four study-specific Follow-Up visits will occur in the first 12 weeks.

(Visit 2 Week 1 ±3 days, Visit 3 Week 2 ±3 days, Visit 4 Week 3 ±3 days, Visit 5 Weeks 4-12)

⁵ The NGS Report is only received once during the 12 week follow-up, typically within 14 days.

⁶ Medical records & imaging results are only requested if attempts to reach the subject for follow-up have been unsuccessful, otherwise, data captured on disease progression and treatment changes are subject-reported.

⁷ 3 month visit windows include Visit 6 (3 months +1 month), Visits 7-12 (6,9,12,15,18,21 months ±1 month), Visit 13 (24 months -1 month)

Title: Study of Plasma Next Generation Sequencing for Remote Assessment, Characterization, Evaluation of Patients With ALK Drug Resistance (SPACEWALK)

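### Section 8.1 sets out to analyse the impact of plasma NGS on treatment choice, but no section describes recording the therapy planned before the report, so the described data support only an association

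*Combined protocol and SAP*

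**What the plan says.** Two passages state the aim, in different strengths. Section 8.1 uses causal wording: "We also plan to analyze if plasma NGS results have any impact on the treatment decision process". Section 7.2 is associational: "To study the relationship between plasma NGS results from plasma specimens to advanced ALK positive NSCLC subjects on progression to a next generation ALK TKI", to be set against treatment decisions. Section 8.1 also describes a correlation analysis in which baseline resistance mechanisms, "treatments received before and after plasma NGS assessments and outcomes will be analyzed".

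The data described are these:
- Intake Form (Section 10.2.2): besides contact details, "Subjects will also be asked to provide pathology reports, medication information and progression information if available".
- Questionnaire (Section 10.4): "demographics, current condition, cancer history, and exposure history".
- CRF (Section 10.5): "Treatment history: dates of previous surgery, radiotherapy, chemotherapy and targeted therapy", along with prior genotyping results.
- Follow-up (Section 10.8): whether and when a new treatment begins, and later its outcome. Under footnote 6 of the Study Calendar (Section 10.11), this is reported by the subject unless the subject cannot be reached.

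On timing, the calendar says: "The NGS Report is only received once during the 12 week follow-up, typically within 14 days". Section 10.3.1 returns results to the subject and the treating physician. Section 9.1 requires that no new line has begun before consent and that blood is given before the new line starts. It does not require the result to be available first. Section 12 gives no endpoint, test or precision for treatment decisions.

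**The concern.** To say that a report had an impact on a choice, one needs to know what would have been chosen without it. That can come from a group with no report or from each subject's plan recorded beforehand. The documents describe neither. A subject who starts a drug that the report calls likely to work looks the same in the data whether the report changed the choice or the physician had already made it.

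At stake is how a secondary aim is read. The analysis would return an association between NGS result and therapy received. Under the wording of Section 8.1, that association could be published as evidence that the test changed management, even if it changed nothing.

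**Working it through.** The plan gives no figure for this aim, so there is nothing to reproduce. The check has three parts.

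**1. Is there a source for the pre-report plan?** The described contents of the Intake Form, questionnaire, CRF and follow-up contacts cover the past and what was started. None lists an intended therapy, the reason for a choice, or a form for the physician's decision. Because all results are returned, there is no concurrent group without a report. Subjects with a negative or unevaluable result do not fill the gap: they also receive a report, and those without a detected rearrangement differ in how much tumour DNA they shed.

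**2. Could the pre-report plan be taken as unrelated to the result?** The protocol's own text argues against it. Section 5.1 expects most patients to receive several lines of different ALK TKIs, so a switch is likely with or without a report. Section 10.5 collects prior genotyping, so a choice may rest on an earlier test. Section 9.1 and the typical 14-day turnaround together allow therapy to start before the report exists.

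**3. What do the data identify?** Let c be the observed share who start a result-matched therapy (one the report describes as likely active against the detected mutation). Let q be the unrecorded share for whom such a therapy was already planned.
- Net impact = c - q.
- The share whose matched status changed lies between |c - q| and min(c + q, 2 - c - q).

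With c = 70% (assumed, not from the documents):

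| q (assumed) | Net impact, points | Share whose matched status changed |
|---|---|---|
| 0% | 70 - 0 = +70 | 70% |
| 30% | 70 - 30 = +40 | 40% to 100% |
| 50% | 70 - 50 = +20 | 20% to 80% |
| 70% | 70 - 70 = 0 | 0% to 60% |
| 90% | 70 - 90 = -20 | 20% to 40% |

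The upper limits come from the second formula; for q = 30%, min(100, 200 - 100) = 100%. Every row fits the same observed 70%. More subjects do not help, because a larger sample estimates c more precisely and says nothing about q. The matched share is also not a ceiling on change, since a switch away from a matched drug counts as well.

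**The case against.** The strongest reply is that the formal objective in Section 7.2 asks only for a relationship, that Section 8.1 itself plans a correlation, and that the described data can estimate both. This stands. A reader might infer that the secondary objective cannot be met; the documents do not support that. The gap is confined to the 'impact' sentence in Section 8.1, which Section 12 supports with no endpoint or sample size.

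Second, a reader might infer that the planned therapy is never recorded. That cannot be shown. Appendices B (questionnaire) and J (Intake Form) are listed, but their text is not in the documents. The medication information on the Intake Form, the interview and record review in Section 10.5, or the records requested at screening might contain a plan for some subjects. What can be said is that no section describes collecting it, dating it against the report, or analysing it.

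Third, recording the plan adds no comparison group. A change from plan may follow drug access, symptoms or a new scan. This also stands, and it limits what the added item may be said to show.

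Fourth, the item may come late. Enrollment opened under Amendment #4 of 20DEC2018 and Section 12.2 plans 24 months of accrual; this version is dated 03FEB2021. Actual accrual is not given. It would be tempting to quote a confidence interval width for all 300 subjects, but the item reaches only those enrolled after the change, and their number is unknown.

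**Conclusion.** The concern holds in a limited form. As described, the data can support an association between NGS result and therapy received. They cannot support a statement that the result had an impact on the choice. The size of any impact is not identified: in the illustration, one observed share of 70% is compatible with a net effect from +70 to -20 points as q runs from 0% to 90%. Those values are assumptions chosen to show the range.

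No precision figure should be attached to the remedy, since neither the number of later enrollees nor the share with a known plan is in the documents. The conclusion rests on the described contents of the forms. If Appendix B or J already asks for the planned therapy before the report, what remains is to define the analysis. The primary objective in Section 7.1 does not depend on this point.

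**What to change.** 1. Add one dated item, 'next systemic therapy planned by the treating physician, if known', to the Intake Form and to the Visit 2 (Week 1) contact. Count it only if its date precedes the report.
2. In Section 12, define the measure as the share whose started therapy differs from that plan, by NGS result, with 'undecided' as its own category. Call it change from plan rather than impact, because the report is not the only possible cause.
3. Compare the report date with the therapy start date. Analyse starts before the report separately, as choices that the report did not influence.
4. For subjects already enrolled, or for everyone if the item is not added, reword the Section 8.1 sentence as a descriptive association between NGS result and therapy received.

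The cost is one field on a form and a contact that already exist, with IRB approval of the change. It needs no extra visit and no change in sample size. The drawbacks are that some answers will be 'undecided' and that only later enrollees contribute. Step 4 alone requires no new data.

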8.2 CORRELATIVE STUDIES

In addition to ALK rearrangement and ALK mutation assessment, plasma NGS can provide dynamic information about treatment effect. Because it is now possible to have genomic information about a wide range of genes through the same plasma NGS assay, we will also explore the relationship between other genomic alterations (e.g. mutations in p53, KRAS, EGFR or MET) with ALK TKI resistance and subject outcomes. We propose to use additional optional plasma NGS assessments after (a) 2-3 weeks of the next therapy initiated after baseline plasma NGS and (b) at disease progression or treatment discontinuation to explore plasma NGS as a biomarker for tumor response.

Role of archival tissue: In order to better understand novel or conflicting liquid biopsy results, we may need to request prior biopsy tissue to perform somatic tumor sequencing. This is expected to be requested on a case by case basis. No additional biopsy will be necessary on study. Tumor specimens will be labelled with the Subject Identification Number and any genomic analysis will be considered investigational, with no results returned to the subject.

Title: Study of Plasma Next Generation Sequencing for Remote Assessment, Characterization, Evaluation of Patients With ALK Drug Resistance (SPACEWALK)

9 STUDY POPULATION

9.1 INCLUSION CRITERIA

- Men or women older than 18 years old at the time of consent or age of majority for residential state.
- Demonstration of having advanced ALK positive NSCLC.
- Systemic progression (not CNS only progression) within the past 30 days, having previously been treated with a next-generation ALK TKI.
- Patient must not have started a new line of therapy before signing the informed consent form.
- Willingness to provide a blood specimen prior to the initiation of a new line of treatment.
- Willingness to provide clinical and medical information to the study team as required.
- Ability to read, write and communicate in English.
- Ability to sign a web-based informed consent form.

9.2 EXCLUSION CRITERIA

- Participants who are unable to provide informed consent.
- Participants who are 18 years of age or younger or less than the age of majority for their state of residence.
- Participants who are unable to comply with the study procedures.
- Known existence of an uncontrolled intercurrent illness including, but not limited to, psychiatric illness or social situations that would impair compliance with study requirements.
- Participants who have previously enrolled to the study.

9.3 INCLUSION OF WOMEN & MINORITIES

Both men and women of all races and ethnic groups are eligible for this trial.

10 STUDY PROCEDURES

10.1 STUDY WEBSITE

Patients will find information about the study on the study-specific website <https://www.alcml.net/SPACEWALK>. The website will include a description of the study, aims, how to participate, and details for contacting the study team. The trial will also be posted on www.clinicaltrials.gov. Physicians and advocacy groups are invited to refer interested patients to the study website.

10.2 INFORMED CONSENT PROCESS

To consent, the potential participant will fill out a Contact Form on the website or call the study-specific phone number. The study team will then send potentially eligible participants a link to view the consent form that is hosted on Vanderbilt Institute for Clinical and Translational Research's RedCap platform. The

**Title: Study of Plasma Next Generation Sequencing for Remote Assessment,
Characterization, Evaluation of Patients With ALK Drug Resistance (**SPACEWALK**)**

study team can provide potential participants a copy of the consent form via mail or email to review, however, consent is obtained through electronic signature on the RedCap platform. Study staff will be available by phone to assist with any questions that arise during the consent process.

RedCap is an electronic informed consent tool available through a secure cloud-based portal that can be accessed from most devices that have an internet connection (e.g. tablet or desktop computer). RedCap takes the Word version of the IRB-approved informed consent document and builds an electronic form that is viewed within the portal. The electronic form has controls placed to capture signatures, dates, names and choices using check boxes or radio buttons.

This technology allows investigators and research staff to respect individual privacy and promote understanding by allowing potential participants to choose their preferred location when reviewing the consent materials and discussing those materials with family or their regular doctor. Potential participants can pose questions to the study team via phone or email.

RedCap ensures appropriate consent documentation. After logging into the RedCap portal, which is accessed via specific URL and individual login credentials, the participant or signatory reviews the electronic consent form and may provide an electronic signature by signing their name with a mouse or their finger. This electronic signature is date stamped. The consent form cannot be finalized until all required signatures are obtained. Once the form is finalized, the portal dashboard displays the certified PDF of the signed consent form that is encrypted, password-protected, and cannot be altered. Participants have immediate access to the signed form within the portal and may view, download, and print the form at any time.

RedCap is in full compliance with HIPAA Security Rules (or HIPAA/HITECH).

In the rare situation a potential participant is unable to sign the online consent (e.g. due to technical difficulties), the study team may mail a paper consent form to the potential participant and proceed with a paper-based process until the participant's technical difficulties have resolved at which time, the online consent will also be signed.

10.2.1 Study Hotline

The sponsor has provided a study-specific phone number to facilitate the recruitment process. The phone number is [name] [contact]). The hotline is available 6am-11pm EST, 7 days per week to individuals interested in participating in the study. The Hotline staff are responsible for:

- responding to unique patient calls on the day received
- answering study-related questions
- releasing online consent form to appropriate potential participants
- being available to assist with technical issues related to the online consent platform
- communicating each patient interaction to the DFCI study team via email

The Hotline staff are not responsible for providing medical advice, consenting study participants or study-related activities. The Hotline staff will only respond to patient calls and will not make any unsolicited calls.

**Title: Study of Plasma Next Generation Sequencing for Remote Assessment,
Characterization, Evaluation of Patients With ALK Drug Resistance (SPACEWALK)**

10.2.2 Intake Form & Medical Record Release Form

After signing the consent form, study participants will be immediately presented with an electronic version of the Intake Form and Medical Record Release Form. The subject can choose to electronically complete the forms or receive them email as described below.

Participants can also receive a screening email (Appendix I) from the study team with an Intake Form (Appendix J) and Medical Record Release Form (Appendix D). The Intake Form collects the subject's contact information, emergency contact information and the treating physician's contact information. Subjects will also be asked to provide pathology reports, medication information and progression information if available. The Medical Record Release Form is DFCI's standard form for obtaining patients' outside hospital medical records.

Upon completing the Intake Form and Medical Record Release Form, subjects will be screened for eligibility by study staff. If eligible, subjects will be registered into the ALCMI's study-specific data repository and assigned a unique subject identification number (see Section 10.2.3). Subjects will also be registered into DFCI's Clinical Trials Management System (CTMS) as per the institution's standard process.

ALCMI's data repository will release an email notification of a new subject to the appropriate study team members such as the study coordinator and Principal Investigator.

